622 **3.4 Training for Group Continuing CLC Use After Using CLC in the Original
623 Study**

624 No additional system training is required for these participants. However, at the discretion of the
625 investigator, refresher training may be provided using a subset of the topics described in section
626 3.2.1 above.

627 **3.5 Blood Glucose and Ketone Testing**

628 Participants will receive supplies for blood glucose and ketone testing as needed and will be
629 provided Hypoglycemia, Hyperglycemia and Ketone Guidelines as detailed in section 4.2.

630 Participants will be required to have a home glucagon emergency kit. Participants who currently
631 do not have one will be given a prescription for the glucagon emergency kit.

632 **3.6 Menstrual Cycle Data Collection**

633 Participants who consent to participate in the collection of menstrual cycle data will be asked to
634 install a Menstrual Cycle tracking app on their personal phones.

635 These participants will be given instructions on how to use the app to collect the desired
636 menstrual cycle data information and will use the app to collect these data on an ongoing basis
637 until the study Final Visit. The data collected will include details about contraception method
638 and menses dates.

639 **3.7 Optimization of Insulin Pump Settings**

640 Data-driven optimization of pump settings will occur at the following times:

- 641 ◆ Screening
- 642 ◆ At the 1- and 2-Week phone contacts for those participants participating in the
643 Extension Phase who switched from SAP to CLC or from CLC to PLGS
- 644 ◆ If the study participant contacts the study physician due to concerns about their pump
645 settings due to recurring hypo- or hyperglycemia.

646 Data will be obtained from CGM and/or pump downloads at the visit. Adjustments to pump
647 settings (basal rates, correction factor, insulin-to-carbohydrate ratio, etc.) will be made in
648 response to major trends observed in the CGM data, with flexibility for clinicians to adhere to
649 guidelines and practices established at each individual practice rather than a fixed set of
650 heuristics for all sites.

651 **3.8 Phone Contacts and Study Visits**

652 Participants will be provided with contact information and will be asked to call the study
653 clinical staff for any health related issues and for technical issues with study system components.
654 Participants will be provided with sufficient study supplies to last until the 13-Week visit.

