1222 As the sample size for objective 1 is determined by the preceding RCT and a variance estimate
1223 for both the group continuing CLC and the group switching to PLGS is not known (no prior data
1224 available to estimate), a power calculation has not been performed.

1225 8.3 Outcome Measures

- 1226 • CGM Metrics
 - 1227 • Overall Control and Hyperglycemia

- 1228 ○ CGM-measured % in range 70-180 mg/dL.
- 1229 ○ CGM-measured % above 180 mg/dL
- 1230 ○ CGM-measured mean glucose
- 1231 ○ % >250 mg/dL
- 1232 ○ % >300 mg/dL
- 1233 ○ high blood glucose index
- 1234 ○ % in range 70-140 mg/dL
- 1235
- 1236 • Hypoglycemia
 - 1237 ○ % below 70 mg/dL
 - 1238 ○ % below 54 mg/dL
 - 1239 ○ % <60 mg/dL
 - 1240 ○ low blood glucose index
 - 1241 ○ hypoglycemia events (defined as at least 15 consecutive minutes <70 mg/dL)
- 1242
- 1243 • Glucose variability
 - 1244 ○ Coefficient of variation (CV)
 - 1245 ○ Standard deviation (SD)
- 1246
- 1247 The last 3 months of the Original RCT Study will be used to calculate baseline CGM metrics for
- 1248 the extension study. CGM data starting from randomization into the extension through the 3
- 1249 month visit will be included in the calculation of each CGM metric. Each metric will be
- 1250 calculated giving equal weight to each CGM reading for each participant. CGM metrics will be
- 1251 computed overall and all for daytime (6am-12mn) and nighttime (12mn-6am) by time of day.
- 1252
- 1253 HbA1c
 - 1254 • HbA1c at 13 weeks
 - 1255 • HbA1c <7.0% at 13 weeks
 - 1256 • HbA1c <7.5% at 13 weeks
 - 1257 • HbA1c improvement from baseline to 13 weeks >0.5%
 - 1258 • HbA1c improvement from baseline to 13 weeks >1.0%
 - 1259 • HbA1c relative improvement from baseline to 13 weeks >10%
 - 1260 • HbA1c improvement from baseline to 13 weeks >1.0% or HbA1c <7.0% at 13 weeks

1261 Questionnaires:

- 1262 • Fear of Hypoglycemia Survey (HFS-II) – total score and 3 subscales:
 - 1263 ◆ Behavior (avoid)
 - 1264 ◆ Behavior (maintain high BG)
 - 1265 ◆ Worry
- 1266 • Hyperglycemia Avoidance Scale – total score and 4 subscales:
 - 1267 ◆ Immediate action
 - 1268 ◆ Worry
 - 1269 ◆ Low BG preference
 - 1270 ◆ Avoid extremes
- 1271 • Diabetes Distress Scale – total score and 4 subscales:
 - 1272 ◆ Emotional burden
 - 1273 ◆ Physician-related distress
 - 1274 ◆ Regimen-related distress
 - 1275 ◆ Interpersonal distress
- 1276 • Hypoglycemia Confidence Scale – total score
- 1277 • Clarke Hypoglycemia Awareness Scores
- 1278 • INSPIRE survey scores

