1434 1 comparing 3 months of PLGS baseline to 3 months of CLC follow up using paired t-tests
1435 unless the data are highly skewed in which case a transformation or a robust statistical method
1436 will be used instead.

1437 Safety outcomes will be tabulated. Device issues, protocol adherence, and the other variables
1438 listed above for tabulation will be described or summarized as indicated.

1439

1440 **Chapter 9: Data Collection and Monitoring**

1441 **9.1 Case Report Forms and Device Data**

1442 The main study data are collected through a combination of electronic case report forms
1443 (CRFs) and electronic device data files obtained from the study software and individual
1444 hardware components. These electronic device files and electronic CRFs from the study
1445 website are considered the primary source documentation.

1446 When data are directly collected in electronic case report forms, this will be considered the
1447 source data. Each participating site will maintain appropriate medical and research records for
1448 this trial, in compliance with ICH E6 and regulatory and institutional requirements for the
1449 protection of confidentiality of participants.

1450 **9.2 Study Records Retention**

1451 Study documents should be retained for a minimum of 2 years after the last approval of a
1452 marketing application in an ICH region and until there are no pending or contemplated marketing
1453 applications in an ICH region or until at least 2 years have elapsed since the formal
1454 discontinuation of clinical development of the investigational product. These documents should
1455 be retained for a longer period, however, if required by local regulations. No records will be
1456 destroyed without the written consent of the sponsor, if applicable. It is the responsibility of the
1457 sponsor to inform the investigator when these documents no longer need to be retained.

1458 **9.3 Quality Assurance and Monitoring**

1459 Designated personnel from the Coordinating Center will be responsible for maintaining quality
1460 assurance (QA) and quality control (QC) systems to ensure that the clinical portion of the trial is
1461 conducted and data are generated, documented and reported in compliance with the protocol,
1462 Good Clinical Practice (GCP) and the applicable regulatory requirements. Adverse events will
1463 be prioritized for monitoring.

1464 A risk-based monitoring (RBM) plan will be developed and revised as needed during the course

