Study Design	
Objective 1: RCT with 1:1 randomization to intervention with CLC vs. PLGS for 3 months.
 
Objective 2: Observational study of initiation and use of CLC for 3 months.
 
Objective 3: Observational study of initiation and use of CLC for 3 months following use of PLGS for 3 months; use of CLC by all participants between end of 3-month period and the point that the system becomes commercially available in order to gather additional safety data.

Number of Sites	Seven US clinical sites
Primary Endpoint	
Objective 1: The primary efficacy outcome for the RCT is time in target range 70-180 mg/dL measured by CGM in CLC group vs. PLGS group over 3 months. Safety outcomes also will be assessed
 
Objective 2: The primary outcome is safety outcomes. Efficacy also will be assessed as a pre-post within participant analysis
 
Objective 3: The primary outcome is safety outcomes. Efficacy also will be assessed as a pre-post within participant analysis

Population	
Key Inclusion Criteria
 
• Successfully completed the original 6-month RCT within the prior 14 days 
Key Exclusion Criteria
 
• Use of any non-insulin glucose-lowering agents except metformin
Sample Size	Sample size is based on the number in the original RCT who successfully complete six months and sign consent to participate in this study (up to approximately 168 total).
Treatment Groups	
Objective 1
 
• Group 1: t:slim X2 with Control-IQ Technology and Study CGM• Group 2: t:slim X2 with Basal-IQ Technology and Study CGM

PARTICIPANT AREA	DESCRIPTION
Participant Duration Protocol Overview/Synopsis	3 months Eligible participants in the original RCT who agree to be part of the Extension Study will sign the informed consent form. 
 • Participants assigned to the original RCT SAP group will initiate use of the CLC system for 3 months. • Participants assigned to the original RCT CLC group will be randomly assigned 1:1 to either continue CLC or switch to PLGS for 3 months. • After 3 months, all participants will be given the opportunity to use the CLC system until the point that the system becomes commercially available

13

14

15 The following table provides an overview of the schedule of study visits, phone contacts, and key
16 procedures.

17

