199 additionally including factors potentially associated with the outcome for which there is an
200 imbalance between groups (assessed based on clinical judgement reviewing the distributions in the
201 two treatment arms, not on a p-value).
202 • Missing Data: As noted above, all subjects will be included in primary analyses and any missing
203 post-randomization data will be handled using direct likelihood. It is also worth emphasizing that
204 any statistical method for handling missing data makes a number of untestable assumptions. The
205 goal will be to minimize the amount of missing data in this study so that results and conclusions will
206 not be sensitive to which statistical method is used. To that end, sensitivity analyses will be
207 performed to explore whether results are similar for primary analysis when using different
208 methods. The following methods will be applied:
209 ○ Direct likelihood
210 ○ Rubin's multiple imputation
211 ○ Available cases only

212
213
214

215 **2.4. Primary and other CGM Metrics Analyses**

216
217 This study primary outcome is CGM measured % time in range 70-180 mg/dL over 13 weeks.
218
219 Summary statistics (mean \pm SD or median (quartiles)) will be reported for the CGM metrics and for
220 differences from pre-randomization by treatment group.
221 The analyses will be done using direct likelihood. A longitudinal linear regression model will be fit with
222 the metric at baseline and follow-up as the dependent variable. This model will adjust for age as fixed
223 effect and site as a random effect. The analyses will report the point estimate, 95% confidence interval
224 and p-value for the treatment group difference at follow-up. Residual values will be examined for an
225 approximate normal distribution. If residuals are highly skewed, then a transformation or robust
226 statistical method (e.g., non-parametric or M estimation) will be used instead.

227
228

229 **2.5. HbA1c Analyses**

230 Summary statistics (mean \pm SD or n(%)) will be reported for the central lab HbA1c (continuous
231 variable) at randomization and 13-weeks by treatment group. A longitudinal model will be fit using
232 values at randomization and 13 weeks adjusting for age as fixed effect and site as a random effect.
233 Missing data will be handled by direct likelihood in this longitudinal model. This model implicitly
234 adjusts for baseline HbA1c by forcing the treatment groups to have the same mean value at baseline.

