- 370 • Baseline CGM time 70-180 mg/dL
- 371 • Age at randomization
- 372 • Sex
- 373 • Race
- 374 • Clinical site
- 375 • Body mass index at randomization
- 376 • Income, education, and/or insurance status
- 377 • Baseline scores for quality of life, hypoglycemia awareness and fear questionnaires

378
379
380
381
382 **2.14. Multiple Comparison/Multiplicity**

383 All treatment group comparisons analyses will be considered exploratory/hypothesis-generating.
384 Consequently, there will not be a formal adjustment for multiplicity.

385
386
387 **2.15. Additional Tabulations and Analyses**

388 Twenty-four hours profiles with medians and quartiles lines and 4-week interval boxplots and
389 tabulations by treatment arms for:

- 391 • % below 70 mg/dL
- 392 • % above 180 mg/dL

393 • % time in range 70-180 mg/dL

394 • mean glucose

395

396 Among women who consent to collection of the menstrual information, an analysis that compares
397 outcomes at different times during the menstrual cycle will be performed overall and by contraception
398 type for selected CGM and insulin metrics.

399

400
401

3. Objective 2

402 Among individuals who used SAP in the original RCT, to asses efficacy and to obtain additional safety
403 data by initiating use of the Control-IQ system for 3 months.
404

405 **3.1 Outcome Measures**

406 The outcome measures for this objective will be the same as those listed above in Section 2.1.
407

408 **3.2 General Approach**

409

- 410 • All p-values will be two-sided.
- 411 • Standard residual diagnostics will be performed for all analyses. If values are highly skewed,
412 then an alternate transformation, nonparametric, or M estimation methods will be used instead
413 for the primary and secondary outcomes. Previous experience suggests that no transformation,
414 nonparametric, or M estimation analyses will be necessary for % time in range 70-180 mg/dL, %
415 above 180 mg/dL, mean glucose, or HbA1c. Other outcomes like % below 70 mg/dL over 13
416 weeks are skewed; however the differences from baseline are expected to follow a normal
417 distribution and there may be no need for transformation, nonparametric, or M estimation.
- 418 • All enrolled participants with non-missing baseline and post-enrollment data will be included in
419 the primary and secondary analyses.
- 420 • All before/after comparisons analyses will be considered exploratory/hypothesis-generating.

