421 Consequently, there will not be an attempt to adjust for multiplicity.

422

423 **3.3. Analysis Cohorts**

424 **3.3.1 Per-Protocol Analyses**

425

- 426 • Safety outcomes will be reported for all enrolled participants.
- 427 • If more than 5% of participants have fewer than 50% data (or <1,092hr) of post-enrollment CGM
428 data, then selected CGM analyses will be replicated excluding such participants.
- 429 • Selected CGM and HbA1c analyses will be replicated including only those participants who used
the CLC system for >80% overall.

430
431
432
433

434 **3.4. Primary and other CGM Metrics Analyses**

435

436 This study primary outcome is CGM measured % time in range 70-180 mg/dL over 13 weeks.
437

438 Summary statistics (mean \pm SD or median (quartiles)) will be reported for the CGM metrics and for
439 differences from pre-enrollment.

440 The before/after values will be compared using paired t-tests. Paired differences will be examined for an
441 approximate normal distribution. If the differences are highly skewed, then a Wilcoxon signed-rank test
442 will be used instead.

443

444

445 **3.5. HbA1c Analyses**

446 Summary statistics (mean \pm SD or n(%)) will be reported for the central lab HbA1c (continuous
447 variable) at randomization and 13-weeks. If the central lab values are missing, then the local values will
448 be used instead. The before/after values will be compared using paired t-tests. Paired differences will be
449 examined for an approximate normal distribution. If the differences are highly skewed, then a Wilcoxon
450 signed-rank test will be used instead.

451 For the binary HbA1c outcomes listed above, a McNemar test will be used.

452

453

454 **3.6. Questionnaires, Insulin, Weight, and BMI Analyses**

455 For questionnaires, insulin, weight, and BMI metrics comparisons between before/after will be made
456 using similar methods as described above in Section 3.4 for the primary analysis.

457

458

459 **3.7. Safety Analyses**

460 The safety metrics will be the same as those listed above in Section 2.7 and will be analyzed in a similar
461 manner except that there are no treatment groups for this objective and no formal statistical
462 comparisons.

463

464

465 **3.8. Device Issues**

466 Same as above in Section 2.8, except no randomization and no treatment groups.

467

468

469 **3.9. Protocol Adherence and Retention**

470 Same as above in Section 2.9, except no treatment groups.

471

472

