579 Data from follow-up visits occurring in the following windows will be included in analysis:

Visit (Target Date)	Metrics ^a	From Day ^b	Thru Day ^b
13-week visit (91 days) - Baseline	H	78	105
26-week visit of (182 days)– Follow-up	H,I	169	196
every 13 weeks until the end (273, 364, and so on days)– Follow-up	H,I	260, 351, and so on	287, 378, and so on

581 a – H = HbA1c, I = Insulin metrics.

582 b – Days from randomization/enrollment, inclusive.

583

584 **4.2 General Approach**

585 Same as described above in Section 3.2.

587

588 **4.3. Analysis Cohorts**

590 Same as described above in Section 3.3.

591

592 **4.4. Primary and other CGM Metrics Analyses**

593 Analyses will be similar to those described above in Section 3.4 except that p-values will be calculated
594 only for before/after PLGS/CLC comparisons.

598 **4.5. HbA1c Analyses**

599 This analysis will be similar to that described above in Section 3.5 except that p-values will be
600 calculated only for before/after PLGS/CLC comparisons and the “after” HbA1c value will be the local
601 value at the final visit.

602

603

604 **4.6. Questionnaires and Insulin Analyses**

605 Same as above in Section 3.6.

606

607

608 **4.7. Safety Analyses**

609 Same as above Section in 3.7.

610

611

612 **4.8. Device Issues**

613 Same as above in Section 3.8.

614

615

616 **4.9. Protocol Adherence and Retention**

617 Same as above in Section 3.8.

618

619

620 **4.10. Baseline Descriptive Statistics**

621 Baseline demographic and clinical characteristics of the cohort of all 13-week participants will be
622 summarized in a table using summary statistics appropriate to the distribution of each variable.
623 Descriptive statistics will be displayed for the PLGS/CLC cohort and overall.

624

625 Will include:

- 626 • Age at 13-week
- 627 • Gender
- 628 • Race/ethnicity
- 629 • Diabetes duration at 13-week
- 630 • HbA1c at 13-week

631

632

633 **4.11. Other Tabulations**

634
635 Individual listings for each 13-week participant will include the following:

636 • Age, gender, race/ethnicity, duration, and HbA1c at 13-week
637 • New medications

638
639 The following tabulations and analyses will be performed:

640 • Sensor performance metrics (difference, absolute relative difference, and International
641 Organization for Standardization criteria)
642 • % time CGM data available to the system

643

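### The exploratory efficacy p-values for Objectives 2 and 3 rest only on before/after tests; a supportive contrast with the arm that stays on CLC would remove shared drift, with Objective 3 the first to fix

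*SAP*

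**What the plan says.** In what follows, SAP means the statistical analysis plan; the comparator of the original trial is written out as sensor-augmented pump.

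- **Objective 2 (sensor-augmented pump to CLC).** SAP 3.4: "The before/after values will be compared using paired t-tests. Paired differences will be examined for an" (the sentence goes on to a normality check, with the Wilcoxon signed-rank test as fallback). SAP 3.5 does the same for continuous HbA1c and uses McNemar's test for the binary HbA1c outcomes. Protocol 8.10 agrees on paired t-tests.
- **Objective 3 (PLGS to CLC).** SAP 4.4: "Analyses will be similar to those described above in Section 3.4 except that p-values will be calculated" only for the PLGS-to-CLC comparison. Protocol 8.11 describes this as "comparing 3 months of PLGS baseline to 3 months of CLC follow up using paired t-tests".
- **Windows in Objective 3.** SAP 4.1.2 takes the 13 weeks before the 13-week visit as baseline and pools all CGM data after that visit, with no end date. Protocol 3.8.4 lets visits run to 15 months after enrollment.
- **HbA1c in Objective 3.** SAP 4.1.3 takes the central-lab value at baseline (local if missing) and local values at follow-up. SAP 4.5 uses the local value at the final visit.
- **The arm that stays on CLC.** SAP Table 1: "Participants assigned to the original RCT CLC group will be randomly assigned 1:1 to either continue CLC or switch to PLGS for 3 months". Its CGM windows for weeks 0-13 are those of Objective 2 (SAP 2.1.2, 3.1), and it attends the same 13-week and later clinic visits. SAP 2.4 summarizes its change descriptively. No section uses it as comparator for Objective 2 or 3.
- **Status.** SAP Table 1 makes safety the primary outcome of Objectives 2 and 3, with efficacy assessed pre-post. SAP 3.2 labels all before/after comparisons exploratory.

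**The concern.** In a one-group before/after test, the device change coincides with the passage of time. Time in study, changes in pump settings and any net seasonal shift go into the same difference as the device. A p-value from that test concerns the total change and cannot be assigned to CLC.

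Objective 3 adds two differences between the periods that have nothing to do with the device: the follow-up can be several times as long as the baseline, and the HbA1c measurement source changes. Any average offset between central-lab and local values goes straight into the paired difference.

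The PLGS arm had also used CLC for 6 months before PLGS, so its week-13 switch is a return to CLC. SAP section 4 calls it initiation. The arm's own earlier CLC value is already computed as the Objective 1 baseline but is not shown here.

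At stake is how the p-values will be read. SAP section 3 adds assessment of efficacy to the stated aim of Objective 2, and SAP 3.4 calls time in range the primary outcome, so a small p-value could be taken as evidence of a device effect.

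**Working it through.** The documents state no SD, effect size or power for these comparisons, so there is no figure to reproduce. Protocol 8.2 says of Objective 1: "available to estimate), a power calculation has not been performed".

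**Inputs from the documents**
- About 50 participants in Objective 2, and about 100 randomized 1:1 in Objective 1, hence about 50 on PLGS and 50 staying on CLC (protocol 8.2).
- "All p-values will be two-sided" (SAP 3.2).

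**Assumptions**
- Two-sided 5% level. No level is stated; it is inferred from SAP 2.4: "The analyses will report the point estimate, 95% confidence interval".
- SD of change in time in range 6 to 10 percentage points, equal in both arms.
- Shared drift of 1 to 3 points, no device effect, all 50 retained.

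**Step 1. Length of the Objective 3 follow-up.** 15 months − 3 months = about 12 months, against a 13-week baseline. Protocol 3.8.5 allows up to 6 further weeks for the final visit.

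**Step 2. False-positive rate of the paired test under drift.** SE = SD/√50, which is 0.85, 1.13 and 1.41 for SD 6, 8 and 10. With drift d, the test statistic follows a noncentral t with 49 degrees of freedom and noncentrality d/SE.

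| Shared drift | SD 6 | SD 8 | SD 10 |
|---|---|---|---|
| 1 point | 21% | 14% | 11% |
| 2 points | 64% | 41% | 28% |
| 3 points | 93% | 74% | 55% |

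**Step 3. The same drift in a difference in change.** Drift common to both arms cancels. In 20,000 simulated trials per drift value at SD 8, with drift from 0 to 3 points, the contrast rejected 4.6% to 5.4% of the time.

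**Step 4. Price in precision.** SE = SD × √(1/50 + 1/50), so the ratio to the paired SE is √2 = 1.41. If only 40 comparators remain, it is √(1 + 50/40) = 1.50.
- 95% half-width, paired: 2.010 × 0.849 = 1.7 points at SD 6; 2.010 × 1.414 = 2.8 at SD 10.
- 95% half-width, contrast: 1.984 × 1.20 = 2.4 at SD 6; 1.984 × 2.00 = 4.0 at SD 10.
- Power for a 5-point effect at SD 10 (noncentral t): 0.93 paired, 0.70 for the contrast. At SD 8: 0.99 and 0.87.

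**Step 5. When the contrast has the smaller mean squared error.** It does when 2·SD²/50 < SD²/50 + d², that is, when d > SD/√50: 0.85 points at SD 6 and 1.4 points at SD 10. Below that drift the paired estimate is the better one.

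**The case against.** The strongest reply is that the paired test does what the plan asks. Objectives 2 and 3 are observational, safety comes first, efficacy is described as pre-post, and no passage attributes the change to CLC. That stands, and it limits the point to a supportive analysis and a sentence on interpretation. It does not remove the point: the exploratory label is used in SAP 3.2 to justify not adjusting for multiplicity, which is a different matter from confounding.

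A reader might go further and infer that the continuing arm is a free, like-for-like control that should replace the paired test. The documents do not support this:

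- **Contacts differ.** Under protocol 3.7, "Data-driven optimization of pump settings will occur at the following times", and the 1- and 2-week occasions are for switchers only. The calls themselves are also for switchers only (protocol 3.8.1), and system training is required only for them (protocol 3.2-3.4). The Objective 2 contrast would include all of this. In Objective 3 those calls fall in the PLGS baseline period.
- **It overlaps with existing comparisons.** PLGS-to-CLC change minus CLC-to-CLC change equals the arm difference after week 13 minus the arm difference in weeks 0-13. If the arms are alike once both use CLC, this is the Objective 1 result with its sign reversed. The Objective 2 contrast likewise draws on the original trial's comparison, among completers who consented.
- **Randomization does not fully protect it.** Continuing after week 13 is optional (protocol 3.8.3), and both contrasts need parallel trends.
- **It costs precision**, as shown above.

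It is also too strong to say that device and season are fully confounded. Entry follows each participant's own completion of the original trial, and no enrollment dates are given, so seasonal effects may partly average out.

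**Conclusion.** The point holds as a cheap improvement of minor severity. The p-values for Objectives 2 and 3 come only from uncontrolled before/after tests, and a shared shift enters those estimates one-for-one. The paired tests are valid for within-person change, but their p-values alone do not isolate a device effect.

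Objective 3 comes first, because its problems can be read directly from the documents: an open-ended follow-up that disagrees with protocol 8.11, and a change of HbA1c source. The inflated false-positive rates are conditional on assumed drift and SD. Nothing in the documents shows that drift of 1 to 3 points occurs.

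The reading that the trial cannot address efficacy in these groups, or that the paired results should be dropped, goes beyond the documents. Randomized comparisons already exist in Objective 1 and in the original trial, and the proposed contrast has limits of its own.

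**What to change.** Amend SAP 3.4-3.5 and 4.4-4.5, taking Objective 3 first:

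1. Keep the paired analyses, and state that their p-values alone do not isolate a device effect.
2. Beside them, report the difference in change versus the arm that stays on CLC, over identical windows in both groups, adjusted for age and site as in SAP 2.4.
3. For Objective 3, use a 13-week follow-up block, in line with protocol 8.11. Longer follow-up can be summarized separately.
4. For HbA1c, use the same source in both groups at each time point, so that a shared central-to-local offset cancels. A local value is also taken at the 13-week visit (protocol 3.8.3), so a local-to-local change is available.
5. Show the PLGS arm's own pre-extension CLC value, and describe its week-13 switch as re-initiation.
6. State the limits: parallel trends; optional continuation after week 13; training, calls and pump-setting optimization specific to switchers in Objective 2; and overlap with Objective 1 and the original trial.

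The cost is SAP wording and one extra model per outcome, with no new data. The added contrast has a standard error about 1.4 times that of the paired estimate, or about 1.5 times if only 40 comparators remain.
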